10.3 Haematological Parameters

The following parameters must be met on the **first day of a new cycle** (other than cycle one, when the inclusion for initial registration parameters must be met):

- Platelet count $\geq 50 \times 10^9/L$, Haemoglobin $\geq 8g/dl$, (prior red blood cell transfusion or recombinant Human Erythropoietin usage is allowed), ANC $\geq 1 \times 10^9/L$.

On any day of Carfilzomib administration **during a cycle** (other than day one of each cycle), the haematological results must be:

- Platelet count $\geq 25 \times 10^9/L$, Haemoglobin $\geq 8g/dl$ (prior red blood cell transfusion or recombinant Human Erythropoietin usage is allowed), ANC $\geq 0.75 \times 10^9/L$.

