10.2 Subsequent cycles (all patients)

In summary treatment should be delayed for any patient experiencing:

- Grade 4 thrombocytopenia with active bleeding
Grade 4 anaemia and Grade 4 thrombocytopenia (without active bleeding) do not require the Carfilzomib dose to be withheld. Participants should receive supportive measures in accordance with institutional guidelines.
- Grade 4 neutropenia or neutropenic fever
- Grade 3/4 non-haematological toxicity

Treatment should continue to be withheld until the neutrophil count and platelet count return to $\geq 0.75 \times 10^9/L$ and $\geq 25 \times 10^9/L$, respectively (during a cycle). Drug-induced non-haematological toxicities have to have reached baseline, or become Grade ≤ 1 prior to re-treatment. Treatment may be delayed up to 8 days to allow sufficient time for recovery from toxicities. Please check table 3 and table 5 for dose reduction guidelines.

If the haematological or non-haematological AE has not resolved within 14 days the patient must discontinue from therapy, if the haematological or non-haematological toxicities have resolved within 14 days, the patient may have their therapy re-instituted at the next lowest dose level. Please check table 3 and table 5 for dose reduction guidelines.

A dose delay of up to 14 days (up to 3 weeks for infection treatment) is permitted at the beginning of a cycle to allow resolution of toxicity. If there is no resolution of toxicity as stated above after 2 weeks of withholding treatment (3 weeks for infection treatment), the participant will be discontinued from treatment. Withholding treatment for more than 2 weeks for other reasons, eg elective surgery such as vertebroplasty, may be permitted after discussion with the CI.

No more than three dose reductions or delays in two consecutive cycles will be permitted in an individual participant on study. If toxicity continues or recurs after three dose reductions or delays, the participant should be discontinued from treatment.

If a patient vomits after taking a dose of an oral agent, no repeat dose should be taken and patient will continue as per schedule but the clinical team should consider prophylactic antiemetics.

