All previously established or new toxicities observed at any time, with the exception of neuropathic pain and peripheral sensory neuropathy, are to be managed as detailed in table 3 recommended action for haematologic toxicities and table 5 dose adjustment guidelines for non-haematological toxicities.

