10.4 Dose Reduction For Haematologic Toxicities

Patients will have a FBC prior to each dose of Carfilzomib during treatment.

Carfilzomib will be withheld from participants with:

- Grade 4 thrombocytopenia with active bleeding
- Grade 4 neutropenia

The following table outlines the dose reduction guidelines for Carfilzomib for thrombocytopenia and neutropenia:

Table 3: Recommended Action for Haematologic Toxicities

Haematologic Toxicity	Recommended Action	
Thrombocytopenia		
When platelets fall to $\leq 25 \times 10^9 / L$	If platelets $10 - 25 \times 10^9 / L$ without evidence of bleeding	Continue at same dose
	If evidence of bleeding or platelets $< 10 \times 10^9 / L$	Withhold dose until platelets return to $\geq 10 \times 10^9 / L$ and/or bleeding is controlled, then resume at same dose.
For each subsequent drop to $\leq 25 \times 10^9 / L$	If platelets $10 - 25 \times 10^9 / L$ without evidence of bleeding	Continue at same dose
	If evidence of bleeding or platelets $< 10 \times 10^9 / L$	Withhold dose until platelets return to $\geq 10 \times 10^9 / L$ and/or bleeding is controlled, then resume at 1 dose decrement
Neutropenia		
When ANC falls to $\leq 0.75 \times 10^9 / L$	If ANC $0.5-0.75 \times 10^9 / L$	Continue at same dose

	If ANC $< 0.5 \times 10^9 / L$	Withhold dose until ANC returns to $\geq 0.5 \times 10^9 / L$, then resume at same dose.
For each subsequent drop to $\leq 0.75 \times 10^9 / L$	If ANC $0.5-0.75 \times 10^9 / L$	Continue at same dose
	If ANC $< 0.5 \times 10^9 / L$	Withhold dose until ANC returns to $\geq 0.5 \times 10^9 / L$, then resume at 1 dose decrement.
Neutropenic fever	If $< 1000/mm^3$ and single temperature $> 38.3^{\circ}C$ OR temperature $> 38.0^{\circ}C$ for more than one hour.	Withhold dose until ANC returns to baseline grade, then resume at same dose.

Please note; if doses of carfilzomib need to be delayed then the dexamethasone dose must also be delayed so that it can be taken prior to the carfilzomib dose. Thalidomide can be taken continuously unless there is toxicity directly attributable to Thalidomide.

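### On day 8 and day 15 the protocol both forbids and continues carfilzomib at platelets 10 to <25 without bleeding and at ANC 0.5 to <0.75, and its restart rules disagree

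*Protocol*

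**What the plan says.** Counts are ×10⁹/L throughout.

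- **Protocol 10.3** has separate limits for day 1 of a cycle (platelets 50, ANC 1) and for later carfilzomib days, which are day 8 and day 15. For the later days ("other than day one of each cycle), the haematological results must be") it lists "Platelet count $\geq 25 \times 10^9/L$, Haemoglobin $\geq 8g/dl" and ANC of at least 0.75. Prior transfusion is allowed for haemoglobin.
- **Protocol 10.4, Table 3** has a row "If platelets $10 - 25 \times 10^9 / L$ without evidence of bleeding" and another for ANC 0.5 to 0.75. Both keep the dose going unchanged, on the first drop and on each later one. Its first-drop restart rules are "Withhold dose until platelets return to $\geq 10 \times 10^9 / L$ and/or bleeding is controlled, then resume at same dose" and "Withhold dose until ANC returns to $\geq 0.5 \times 10^9 / L$, then resume at same dose". Later drops restart one dose decrement lower.
- **Protocol 10.4, list before Table 3** ("Carfilzomib will be withheld from participants with") names only grade 4 thrombocytopenia with active bleeding and grade 4 neutropenia.
- **Protocol 10.2** states "Grade 4 anaemia and Grade 4 thrombocytopenia (without active bleeding) do not require the Carfilzomib dose to be withheld". Once a dose is withheld during a cycle, it stays withheld until ANC is 0.75 and platelets are 25, and therapy may then restart at the next lowest dose level. The section caps reductions or delays at three in two consecutive cycles. It closes by sending toxicities to Tables 3 and 5: "All previously established or new toxicities observed at any time".
- **Protocol 10.12** requires a hold at platelets of 10 or below with bleeding, and places the platelet nadir between day 8 and day 15.
- **Non-haematological toxicity:** 10.2 and 10.5 restart at grade 1 or below, or baseline. The row of Table 5 for other carfilzomib-related toxicity restarts at grade 2 or below, or baseline.

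**The concern.** A blood count precedes every carfilzomib dose, so a site that sees platelets of 15 or an ANC of 0.6 on day 8 has to choose between two instructions. Up to 15 centres would make that choice separately, at the visits around the expected platelet nadir.

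Dose delays and relative dose intensity are named secondary endpoints (Protocol 18.2; SAP 2.2). If centres follow different rules, these summaries partly describe which rule was used rather than how well KTD is tolerated. Holds also count towards the cap in 10.2, so the same counts could take one patient to discontinuation and leave another never held. In cycle 1 of escalation, a toxicity delay of more than 8 days is itself a DLT (Protocol 8.1.4, criterion 4).

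**Working it through.** **1. Give or hold on day 8 or day 15, other counts adequate**

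| Count | 10.3 | Table 3 | 10.2 and 10.4 hold lists |
|---|---|---|---|
| Platelets exactly 25, no bleeding | give | give | give |
| Platelets 10 to <25, no bleeding | **hold** | **give, same dose** | no hold |
| Platelets <10, no bleeding | hold | hold | **no hold required** |
| ANC exactly 0.75 | give | give | give |
| ANC 0.5 to <0.75 | **hold** | **give, same dose** | no hold |
| ANC <0.5 | hold | hold | hold |

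Scanning platelets from 0 to 60 in steps of 1, and ANC from 0 to 1.5 in steps of 0.01, gives the same disagreement between 10.3 and Table 3: platelets 10 to 24 and ANC 0.50 to 0.74.

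The row for platelets <10 assumes that such a count is grade 4, because Appendix 5 does not reproduce the platelet grades. There 10.3 and Table 3 agree. The conflict is with 10.2, the 10.4 list and 10.12, which tie the hold to bleeding.

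**2. Restart**

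| | 10.2 | Table 3 | Gap |
|---|---|---|---|
| Platelets | 25 | 10 and/or bleeding controlled | 25 − 10 = 15 |
| ANC | 0.75 | 0.5 | 0.75 − 0.5 = 0.25 |
| Dose level | next lowest | same after first drop | one level |

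**3. Exposure.** Six cycles × 3 doses = 18 planned doses, of which 6 × 2 = 12 fall on day 8 or day 15 (12/18 = 66.7%). In escalation, 10.1 already delays treatment for grade 3 or 4 toxicity after the loading dose. Appendix 5 makes ANC 0.5 to <1.0 grade 3. For the ANC band, cycle 1 day 8 therefore drops out, leaving 11 days.

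**4. Cap in 10.2.** Two consecutive cycles contain 2 × 2 = 4 such days, against a limit of 3. Counts in the two bands give up to 4 holds under 10.3 and 0 under Table 3. Four separate holds need short delays: a day 8 dose delayed by the full 8 days falls on day 16, after the planned day 15 dose.

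**5. Relative dose intensity** (cumulative dose ÷ duration, relative to plan; Protocol 18.3 and 19.4). The protocol does not say whether a held dose is delayed or omitted, or whether the cycle lengthens, so both cases are shown for one held dose from cycle 2 on:
- 8-day delay, cycle lengthened: 28/(28 + 8) = 77.8% in that cycle; over six cycles, 168/(168 + 8) = 95.5%.
- Dose omitted, duration kept: 2/3 = 66.7% in that cycle; over six cycles, 17/18 = 94.4% if all doses are treated as equal. Allowing for the 20 mg/m² loading dose, it runs from 452/479 = 94.4% at 27 mg/m² to 916/972 = 94.2% at 56 mg/m².
- No hold (Table 3): 100%.

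**The case against.** The best defence is that the protocol already routes these counts to Table 3. Its rows open at exactly the in-cycle floors of 10.3, so they can be read as the action to take when 10.3 is not met. The closing paragraph of 10.2 sends toxicities to Table 3, and 2.1.3.1 favours supporting thrombocytopenia over reducing treatment. This stands as a reason to make Table 3 the default, though 2.1.3.1 speaks to platelets only. It does not remove the conflict. Nothing withdraws the mandatory wording of 10.3, and the restart counts in 10.2 side with 10.3. If 10.3 governs, the continue rows of Table 3 operate only at exactly 25 or 0.75. If Table 3 governs, the in-cycle platelet and ANC limits of 10.3 do nothing.

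Three stronger readings are tempting and are not supported:
- **Haemoglobin as a further contradiction.** 10.3 requires 8 g/dl, while 10.2 exempts grade 4 anaemia from a hold. But 10.3 allows prior transfusion, 10.2 calls for supportive measures and 10.12 says to correct anaemia. Transfusing to 8 and then dosing satisfies all three, so only the wording needs clarifying.
- **A large loss of dose intensity.** The 66.7% and 77.8% figures are single-cycle values for one event. Protocol 19.4 also plans overall summaries, where the same event costs about 5 percentage points.
- **A distorted MTD.** This would need a day 15 hold of more than 8 days in cycle 1, judged to be related to treatment, attributed to the registered dose and accepted by the Safety Review Committee.

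It is also fair to say that all analyses are descriptive, and that the grade 3 or 4 toxicity endpoint counts an ANC of 0.5 to <0.75 whether or not the dose is held.

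**Conclusion.** The contradiction is in the current text and should be fixed. It covers give-or-hold at platelets 10 to <25 without bleeding and at ANC 0.5 to <0.75, the restart counts, the restart dose level, and the hold at platelets <10 without bleeding. The mismatch between Table 5 and 10.2/10.5 on non-haematological restart is a separate, smaller inconsistency of the same kind.

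The size is bounded per event: 77.8% or 66.7% intensity in the affected cycle, and about 95.5% or 94.4% over six cycles, against 100% under Table 3. These figures assume one hold and full planned treatment otherwise. A trial-level effect cannot be calculated. The background reports toxicity in other regimens and populations, such as grade 3 neutropenia of about 5% with single-agent carfilzomib in myeloma (2.1.3.2), but no rate for these count bands under KTD. The consequence is mainly for consistent and safe dosing and for the dose-delivery endpoints. An effect on the DLT endpoint is possible but narrow.

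**What to change.** Use one set of in-cycle give, hold and restart thresholds, and one restart dose level, in 10.2, 10.3, 10.4 with Table 3, and 10.12.

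- **Default:** Table 3 governs on day 8 and day 15. Change the in-cycle platelet and ANC limits in 10.3, and the restart counts and dose level in 10.2, to match it. Add platelets <10 without bleeding to the hold lists in 10.2 and 10.4 and to the rule in 10.12.
- **Alternative:** raise the continue and restart cut-offs of Table 3 to 25 and 0.75, and align the restart dose level and hold lists with them.
- The choice is clinical. The default accepts dosing down to platelets of 10, so the clinical team should confirm it after weighing the thromboprophylaxis given to all patients (9.2) and the haemorrhage warning in 10.12.
- Keep the day 1 limits in 10.3. State that haemoglobin is corrected to at least 8 g/dl by transfusion and the dose then given.
- State that 10.1 governs toxicity after the loading dose in escalation.
- Set the Table 5 row for other toxicity to grade 1 or below, or baseline, as 10.2 and 10.5 already say.

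The DLT definition does not change. The cost is a protocol amendment, with approvals as needed under 21.4, and notification of sites. No patients, visits or tests are added.

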10.4 Dose Reduction For Haematologic Toxicities

Patients will have a FBC prior to each dose of Carfilzomib during treatment.

Carfilzomib will be withheld from participants with:

- Grade 4 thrombocytopenia with active bleeding
- Grade 4 neutropenia

The following table outlines the dose reduction guidelines for Carfilzomib for thrombocytopenia and neutropenia:

Table 3: Recommended Action for Haematologic Toxicities

Haematologic Toxicity	Recommended Action	
Thrombocytopenia		
When platelets fall to $\leq 25 \times 10^9 / L$	If platelets $10 - 25 \times 10^9 / L$ without evidence of bleeding	Continue at same dose
	If evidence of bleeding or platelets $< 10 \times 10^9 / L$	Withhold dose until platelets return to $\geq 10 \times 10^9 / L$ and/or bleeding is controlled, then resume at same dose.
For each subsequent drop to $\leq 25 \times 10^9 / L$	If platelets $10 - 25 \times 10^9 / L$ without evidence of bleeding	Continue at same dose
	If evidence of bleeding or platelets $< 10 \times 10^9 / L$	Withhold dose until platelets return to $\geq 10 \times 10^9 / L$ and/or bleeding is controlled, then resume at 1 dose decrement
Neutropenia		
When ANC falls to $\leq 0.75 \times 10^9 / L$	If ANC $0.5-0.75 \times 10^9 / L$	Continue at same dose

	If ANC $< 0.5 \times 10^9 / L$	Withhold dose until ANC returns to $\geq 0.5 \times 10^9 / L$, then resume at same dose.
For each subsequent drop to $\leq 0.75 \times 10^9 / L$	If ANC $0.5-0.75 \times 10^9 / L$	Continue at same dose
	If ANC $< 0.5 \times 10^9 / L$	Withhold dose until ANC returns to $\geq 0.5 \times 10^9 / L$, then resume at 1 dose decrement.
Neutropenic fever	If $< 1000/mm^3$ and single temperature $> 38.3^{\circ}C$ OR temperature $> 38.0^{\circ}C$ for more than one hour.	Withhold dose until ANC returns to baseline grade, then resume at same dose.

Please note; if doses of carfilzomib need to be delayed then the dexamethasone dose must also be delayed so that it can be taken prior to the carfilzomib dose. Thalidomide can be taken continuously unless there is toxicity directly attributable to Thalidomide.

10.5 Dose Reductions for Non-Haematologic Toxicities

Carfilzomib should be withheld for events \geq Grade 3 until resolved to \leq Grade 1 or return to baseline.

After resolution of the event to \leq Grade 1 or return to baseline, if the adverse event was not treatment-related, subsequent treatment with Carfilzomib may resume at full dose. If the event was treatment-related, subsequent treatment with Carfilzomib will resume at one level dose reduction except for nausea, vomiting or diarrhoea which can be attributed to Carfilzomib (see table 5 below). If toxicity continues or recurs, a 2nd Carfilzomib dose reduction may be permitted at the discretion of the investigator. No more than three dose reductions will be permitted in an individual participant on study. If toxicity continues or recurs after three dose reductions, the participant should be discontinued from treatment.

Dose reduction guide for Carfilzomib:

Table 4: Dose Reduction Guide for Carfilzomib Dosing

Current dose	Reduce to
27mg/m ²	20mg/m ²
36 mg/m ²	27 mg/m ²
45 mg/m ²	36 mg/m ²
56 mg/m ²	45 mg/m ²

If the participant tolerates the reduced dose for two cycles, participant may be dose escalated to the dose prior to reduction following discussion with the CI and CTRU.

Dose adjustment guidelines for non-haematologic toxicities are summarised as follows:

Table 5: Dose Adjustment Guidelines for Non-Haematological Toxicities.

Symptom	Recommended Action Carfilzomib
Allergic reaction/hypersensitivity Grade 2 – 3 Grade 4	Withhold until \leq Grade 1, reinstitute at full dose. Discontinue (refer to section 14)
Tumour lysis syndrome (≥ 3 of following: $\geq 50\%$ increase in creatinine, uric acid, or phosphate; $\geq 30\%$ increase in potassium; $\geq 20\%$ decrease in calcium; or ≥ 2 -fold increase in LDH)	Withhold Carfilzomib until all abnormalities in serum chemistries have resolved. Reinstitute at full doses.

Infection Grade 3 or 4	Withhold Carfilzomib until systemic treatment for infection complete and infection resolves. If no neutropenia, restart at same dose. If neutropenic, follow neutropenia instructions.
Herpes zoster of any grade	Withhold Carfilzomib until lesions are dry. Reinstigate at full dose
Grade 3 Nausea or vomiting despite maximal anti-emetic therapy or diarrhoea	Withhold Carfilzomib until this resolves and re-start at full dose. If recurrent, re-start at one dose level lower
Grade 2 treatment emergent neuropathy with pain or Grade 3 neuropathy	Continue to dose. If neuropathy persists for more than two weeks hold Carfilzomib until resolved to \leq Gr 2 without pain. Then restart at 1 dose decrement
\geq Grade 3 elevation in LFTs (AST, ALT, or total bilirubin)	Withhold dose. Resume at 1 dose decrement when toxicity has resolved to baseline.
Grade 4 neuropathy	Discontinue (refer to section 14)
Renal Dysfunction Serum creatinine equal to or greater than 2 x baseline, or CrCl $<$ 15mL/min (or CrCl decreases to \leq 50% of baseline) or need for dialysis.	Withhold dose and continue monitoring renal function (serum creatinine or serum creatinine clearance). If attributable to Carfilzomib, resume when renal function has recovered to within 25% of baseline. Start at 1 dose level reduction. If not attributable to Carfilzomib, dosing may be resumed at the discretion of the physician. If tolerated, the reduced dose may be escalated to the previous dose at the discretion of the physician. For patients on dialysis during Carfilzomib, the dose is to be administered after the dialysis procedure.
Congestive heart failure and other cardiopulmonary disorders.	See section 10.10. Any participant with marked worsening of symptoms of congestive heart failure, whether or not drug related, must have the dose withheld until resolution or return to baseline, after which treatment may continue at a reduced dose, or the subject may be permanently discontinued
Other non-haematologic toxicity assessed as Carfilzomib-related \geq Grade 3	Withhold dose until toxicity resolves to \leq Grade 2 or baseline. Restart at 1 dose decrement. If tolerated, the reduced dose may be escalated to the previous dose at the discretion of the physician.
PRES (posterior reversible encephalopathy syndrome with symptoms including headaches, altered mental status, seizures, visual loss, and hypertension).	If PRES suspected, withhold Carfilzomib. Consider evaluation with neuroradiological imaging for onset of visual or neurological symptoms suggestive of PRES. If PRES diagnosis is excluded, Carfilzomib administration may resume if clinically appropriate.

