10.0 Dose delays and modifications

The dose of Carfilzomib should be delayed and / or reduced according to the guidelines given below (CTCAE v4.03). Dose re-escalation may occur if the toxicities were considered to be disease related, however dose re-escalation should only be undertaken following discussion with the CI.

Please see appendix 8 for known risk and discomforts from Carfilzomib.

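### Table 5 contradicts the section 10 text it summarises on when carfilzomib may restart, and when a reduced dose may be raised again, after a non-haematological toxicity

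*Protocol*

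**What the plan says.** **Restart after withholding.**
- Protocol section 10.2: "Drug-induced non-haematological toxicities have to have reached baseline", or Grade 1 or lower, before re-treatment. It adds: "If the haematological or non-haematological AE has not resolved within 14 days the patient must discontinue from therapy".
- Section 10.5, opening text: carfilzomib is withheld for events of Grade 3 or higher until they have come down to at most "Grade 1 or return to baseline".
- Table 5, row for other carfilzomib-related non-haematological toxicity of Grade 3 or higher (the *Other* row): withhold until at most "Grade 2 or baseline. Restart at 1 dose decrement".

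**Raising a reduced dose again.**
- Section 10.0: "Dose re-escalation may occur if the toxicities were considered to be disease related", and "dose re-escalation should only be undertaken following discussion with the CI".
- Section 10.5, text under Table 4: "If the participant tolerates the reduced dose for two cycles, participant may be dose escalated to the dose prior to reduction", after discussion with the CI and CTRU. No condition on cause is attached.
- Table 5, Renal Dysfunction and *Other* rows: "If tolerated, the reduced dose may be escalated to the previous dose at the discretion of the physician".

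Section 10.2 closes by sending sites to Tables 3 and 5 for managing toxicities. Section 10.5 presents Table 5 as a summary of the dose-adjustment guidelines. Nothing says which prevails if the table and the text disagree.

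**The concern.** A site with a carfilzomib-related event in front of it can follow the text or the table, and the two give different instructions. On restart, the table permits dosing while the toxicity is still at a grade at which the text says to keep withholding. On re-escalation, the table leaves out the two-cycle observation period and CTRU involvement, and it leaves the decision to the treating physician.

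Patient safety comes first. The trial enrols patients with amyloid organ involvement, and its expansion phase exists to characterise tolerability at the recommended dose. Consistency comes second. Patients with the same event could be handled differently at up to 15 sites. That feeds into withdrawals, dose delays and relative dose intensity (section 18.2), and into the primary endpoint of any Grade 3 or 4 toxicity over all cycles (section 18.1).

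**Working it through.** The plan gives no figure to reproduce, so the check is a comparison of rules, followed by simple counting.

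**1. Restart grade.** Take a carfilzomib-related Grade 3 event that falls under the *Other* row, with baseline Grade 0 or 1. The event improves to Grade 2 and stays there.

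| Time | Sections 10.2 and 10.5 | Table 5, *Other* row |
|---|---|---|
| Reaches Grade 2 | Keep withholding | Restart one dose level lower |
| Still Grade 2 at day 14 | Discontinue (10.2) | May already be back on treatment one level lower |

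If baseline is Grade 2 or higher, all three rules allow restart at baseline and the conflict disappears. It therefore applies only to patients whose baseline is below Grade 2. Section 10.1 (cycle 1, dose escalation) and section 10.9 (infections) also use Grade 1 or lower, or baseline, so the *Other* row departs from the general standard.

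**2. Re-escalation.**

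| Source | Time at reduced dose | Who is involved |
|---|---|---|
| 10.0 | Not stated | CI |
| 10.5 text | Two tolerated cycles | CI and CTRU |
| Table 5, Renal and *Other* rows | Tolerated, no duration given | Physician's discretion |

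The section 10.0 requirement for CI discussion is general and can be read as applying to Table 5 too. The two-cycle period and CTRU involvement appear only in the 10.5 text and cannot be read out of the table rows.

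**3. Size of a step.** From Table 4, going back up one level:
- 56/45 = 1.244, or 24%
- 45/36 = 1.250, or 25%
- 36/27 = 1.333, or 33%
- 27/20 = 1.350, or 35%

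**4. Doses that could be affected.** Section 8.1.1 gives 3 carfilzomib doses per cycle and at most 6 cycles. Suppose the reduction takes effect on day 1 of cycle k, with k = 2 to 6.
- Section 10.5 text: return at cycle k + 2, so restored doses = max(0, 3 × (5 − k)) = 9, 6, 3, 0, 0.
- Table 5, assuming tolerance is judged over one full cycle: return at cycle k + 1, so restored doses = 3 × (6 − k) = 12, 9, 6, 3, 0.
- Difference: 3, 3, 3, 3, 0 doses, that is, one cycle at most.

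The one-cycle reading is an assumption, because the table gives no duration. The counts are upper limits. They suppose that treatment runs to cycle 6, whereas non-responders leave trial treatment after three cycles (section 9.4). The documents give no rate for these events, so expected exposure cannot be calculated.

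**The case against.** The best defence is that a specific table overrides general text. Section 10.2 directs sites to Table 5, so they have an operative default, and the tolerance condition may be shorthand for the two-cycle rule just above it. This does not settle the matter. No precedence is stated, and a table introduced as a summary should not relax what it summarises. The *Other* row is a catch-all and not an organ-specific exception such as the neuropathy row. Section 10.2 states its Grade 1 rule and refers to Table 5 in the same paragraph. Shorthand could explain the tolerance wording, but not the missing CTRU step or the restart grade.

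The points about scale do stand. The *Other* row is a residual category: many toxicities have their own Table 5 row, section 10.11 exempts some Grade 3 events from withholding, and section 10.12 treats several others separately. Re-escalation cannot exceed the dose before reduction. Dose alterations and reasons are recorded each cycle (section 11.2), the Safety Review Committee reviews safety, and toxicity after three reductions leads to discontinuation (section 10.5). All analyses are descriptive, with no comparison between arms to distort. These points limit the consequences, but they do not tell a site which rule to follow.

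A reader might infer three stronger points that the documents do not support:
- **That section 10.0 forbids re-escalation after any drug-related toxicity.** Its wording is permissive. It names disease-related toxicity as a case where re-escalation may occur and does not say that this is the only case, while section 10.5 allows it without regard to cause.
- **That Table 5 allows return to the earlier dose after a single tolerated infusion.** No section says so.
- **That the Renal row leaves open which attribution branch its re-escalation sentence covers.** Only the branch for events attributable to carfilzomib specifies a reduction, so the sentence most naturally belongs there. Any remaining doubt is editorial.

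**Conclusion.** The contradiction is real in both places and should be corrected. The restart-grade conflict is the firmer of the two: for the same patient, sections 10.2 and 10.5 say withhold and the *Other* row says restart. The difference is one CTCAE grade, and at 14 days it decides between discontinuing and continuing one level lower. This holds when baseline is below Grade 2 and the event falls in the residual row.

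On re-escalation, the Renal and *Other* rows omit the two-cycle and CTRU conditions of section 10.5. The step is 24% to 35% of the reduced dose. It could come one cycle, or up to three doses, sooner if tolerance is judged over one full cycle.

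MTD determination is not directly affected, because the DLT window closes at the first cycle 2 dose. The sample size is unaffected. The consequences lie in patient safety and consistent dosing for a limited group, namely residual related events plus, for re-escalation, renal events.

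**What to change.** 1. In the *Other* row of Table 5, change the restart threshold to Grade 1 or lower, or baseline.
2. In the Renal and *Other* rows, replace the physician-discretion sentence with a statement that the dose may be re-escalated as in section 10.5 (two tolerated cycles, then discussion with the CI and CTRU).
3. Amend the re-escalation sentence in section 10.0 so that it also refers to the section 10.5 route and does not read as limiting re-escalation to disease-related toxicity. If the trial team does intend that limit, delete the re-escalation sentence from the *Other* row instead of cross-referring it. Otherwise a row confined to carfilzomib-related events would point to a route that section 10.0 closes.

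The cost is a protocol wording amendment and notification to sites, with slightly less local discretion. Some patients held at Grade 2 will wait longer or discontinue at 14 days, as section 10.2 already requires. No extra patients, procedures or CRF fields are needed.
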